9.1.3 Analysis of secondary efficacy endpoints

For evaluation of the following additional efficacy parameters:

- Frequency of hyperechoic linear lesions in post-surgical period based on results of transvaginal ultrasound investigation
- Change in frequency of detecting limited displaceability in comparison to baseline (absolute change and in % of baseline value)
- Change in frequency of detecting hyperechoic linear lesions based on repeated transvaginal ultrasound investigation in comparison to baseline
- Frequency of detecting complete absence of USI – signs of adhesion process in the pelvis in post-surgical period (defined as absence of limited displaceability of pelvic organs and absence of hyperechoic linear lesions)

Respective relative (%) and absolute (number of observations) frequencies as well as accurate 95% binominal CIs will be calculated for each group. For evaluation of difference between each dose

of the drug Seroguard and the placebo, Fisher's exact test will be used as well as accurate 95% CI will be calculated for differences in percentages between the groups.

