4.2.3.6 Instrumental studies

Electrocardiography

Acceptable terms of ECG performance are specified in section 4.2.4.

Standard 12-lead ECG (with measurement of heart rate [HR], PR, QRS, QT intervals and calculation of QTc) will be performed in prone position after 5 minutes of rest. Recording rhythm in the respective leads should contain evaluable data of at least three cardiac cycles. All the changes in ECG should be subjected to evaluation by a primary care physician.

If any changes in ECG, Medical Investigator should evaluate their clinical significance. If clinically significant deviations at screening, Medical Investigator should evaluate possibility of inclusion of patient into the present study, at Visit 2 and 3 or in case of unscheduled visit or withdrawal visit – to evaluate conformity to AR criteria (see section 8.2).

Ultrasound investigation of abdominal cavity and retroperitoneum

It is performed twice at Visits 0 and 2 as well as at withdrawal visit of the study as per the unique method presented in the separate guideline.

Performance of pelvic USI

Pelvic USI is performed at Visits 0 and 3 as well as at withdrawal visit of the study as per the unique method presented in the separate guideline, using transvaginal probe. Video recording of the performed investigation is required! Disc with the study results is attached to the primary documentation.

Performance of MRI of abdominal cavity and pelvis

The study is performed under fasting conditions (a female patient should starve before the investigation for at least 4 hours). 0.5 – 1.0 hours before the investigation, a female patient should

void the bladder and colon. Before the investigation, features of abdominal cavity and pelvic MRI performance will be explained to a female patient in detail.

MRI of the abdominal cavity and the pelvis is performed at Visits 0 and 3, as well as at withdrawal visit as per the protocol of MRI investigation which will be provided in a separate guideline along with evaluation of adhesion severity according to the following method defined by the Sponsor:

Prevalence in abdominal cavity:

1. absence of adhesions;
2. one floor (up to 3 segments of one level);
3. two floors;
4. total adhesive process.

Prevalence in pelvic cavity:

1. Absence;
2. One region (right lateral space, left lateral space, pouch of Douglas or vesicouterine pouch);
3. Two regions;
4. Subtotal adhesive process in the pelvis (3 regions);
5. Total adhesive process in the pelvis.

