5.1 Inclusion criteria

1. Female patients aged from 18 to 45 years with confirmed diagnosis of pelvic adhesions with indications for surgery (laparoscopic adhesiolysis)
2. Voluntarily and personally signed and dated Form of Informed Consent to participate in the study
3. Female patients with pelvic adhesions confirmed by gynecological examination and USI

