9.3 A significance level used

In all the tests, a 5% significance level will be used, whereby a primary endpoint will be analyzed using unilateral test, and bilateral statistical tests will be used for analysis of secondary endpoints.

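### Section 9.1.3 applies exact binomial intervals and Fisher's exact test to two endpoints defined as arm-level change in frequency from baseline, which those methods neither estimate nor test

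*Protocol*

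**What the plan says.** Protocol section 9.1.3 groups four ultrasound endpoints under one analysis. Two are post-surgical frequencies. The other two are changes: "Change in frequency of detecting limited displaceability in comparison to baseline (absolute change and in % of baseline value" and "Change in frequency of detecting hyperechoic linear lesions based on repeated transvaginal ultrasound investigation in comparison to baseline".

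The method is then stated once for the whole list. Within arms: "Respective relative (%) and absolute (number of observations) frequencies as well as accurate 95% binominal CIs will be calculated for each group". Between arms, the sentence on active against control reads in part: "of the drug Seroguard and the placebo, Fisher's exact test will be used as well as accurate 95% CI will be calculated for differences in". The quantity compared is the arm's percentage. Section 9.3 adds that "bilateral statistical tests will be used for analysis of secondary endpoints", at the 5% level.

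The two readings behind each change come from the same woman. Section 4.2.3.6: "Pelvic USI is performed at Visits 0 and 3 as well as at withdrawal visit of the study". The entry criterion in section 5.1 is "Female patients with pelvic adhesions confirmed by gynecological examination and USI". It names neither of the two ultrasound signs, so a woman can be enrolled without one or the other at Visit 0.

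The synopsis and sections 4.1, 7.1 and 9.1.3 all list the change endpoints. None of them defines a yes/no outcome per woman for these endpoints, and no paired or baseline-adjusted method is named.

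**The concern.** An exact binomial interval and a 2×2 table both need a number of women with an outcome out of a number at risk. A change in an arm's detection frequency is not such a number. It can be positive or negative, and when expressed relative to baseline it is a ratio whose denominator is itself random. The stated method therefore does not match the stated endpoint.

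The analyst must choose a substitute, and the candidates answer different questions. At stake is the interpretation of two of the six secondary efficacy endpoints, and a choice between workarounds that could be made after the data are seen.

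**Working it through.** **Inputs.** Planned completers: 24 per arm (section 9.2). Two-sided 5% level (section 9.3). Same women at Visits 0 and 3 (section 4.2.3.6). The protocol gives no expected frequencies for the two signs and no design figure for these endpoints, so there is no stated result to reproduce. All counts and probabilities below are assumptions for illustration.

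**1. What the endpoint is.** In an arm of n women let a have the sign at both visits, b lose it and c gain it.

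- Visit 0 frequency = (a + b)/n; Visit 3 frequency = (a + c)/n.
- Absolute reduction = (b − c)/n, which can lie anywhere from −1 to 1.
- Reduction relative to baseline = (b − c)/(a + b), with a random denominator.
- Paired (Wald) standard error of the absolute reduction = √[b + c − (b − c)²/n] / n.

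The precision depends on b + c, the number of women who switch in either direction. A binomial interval uses only b − c and n.

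**2. Same net reduction, different uncertainty.** Take a net reduction of 12 in 24 (0.50). Treated as 12/24, the exact binomial interval is always 0.29 to 0.71. The paired interval is not constant:

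| Lost b | Gained c | Paired 95% CI |
|---|---|---|
| 12 | 0 | 0.30 to 0.70 |
| 14 | 2 | 0.24 to 0.76 |
| 16 | 4 | 0.19 to 0.81 |
| 18 | 6 | 0.15 to 0.85 |

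For example, with 18 lost and 6 gained: √(24 − 144/24)/24 = √18/24 = 0.177, and 0.50 ± 1.96 × 0.177.

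**3. One data set, several readings.** Arm A goes from 20/24 to 8/24 and arm B from 14/24 to 8/24, with no woman gaining the sign. The absolute changes are −50 and −25 points; relative to baseline they are −12/20 = −60% and −6/14 = −43%.

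- Fisher on Visit 3 status (8/24 v 8/24): p = 1.00.
- Fisher on net change forced into counts (12/24 v 6/24): p = 0.14.
- Fisher on resolution among women with the sign at Visit 0 (12/20 v 6/14): p = 0.49. An exact test stratified by Visit 0 status gives the same value here, because the women without the sign at Visit 0 contribute no events.
- Difference in change, paired: 25 points, SE = √(0.102² + 0.088²) = 0.135, 95% CI −1.5 to 51.5 points.

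Only the last estimates the contrast that the endpoint's wording describes, and section 9.1.3 does not mention it.

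**4. If net changes were put into the stated methods.** Simulation with 24 per arm, 40,000 runs, and the same true change in both arms. Runs with a wrong-sign change are counted as no rejection for the test and as not covered for the interval.

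| P(lose) / P(gain) | Fisher rejects | Exact CI covers | No table possible |
|---|---|---|---|
| 0.30 / 0 | 2.6% | 97.7% | 0% |
| 0.35 / 0.05 | 7.0% | 93.4% | 0.5% |
| 0.40 / 0.10 | 11.1% | 88.8% | 1.6% |
| 0.50 / 0.20 | 17.3% | 80.8% | 4.7% |
| 0.50 / 0.30 | 17.0% | 70.8% | 20.3% |

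Of the scenarios tried, the nominal level holds only in the one where no woman gains the sign; there b − c = b really is a binomial count.

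**The case against.** The best defence is that section 9.1 calls itself a brief description and defers the complete analysis to the statistical analysis plan, where a per-woman variable could be derived. The primary endpoint is also worded as a frequency and is plainly a per-patient response. With a per-woman outcome, Fisher's test and exact intervals are appropriate. This stands in part: the gap is as much an undefined variable as a wrong test. But the primary endpoint states its per-patient threshold and these endpoints state none. A change expressed relative to baseline also has no useful meaning for a single woman's yes/no sign. The protocol has fixed the method here, not left it open.

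A second defence is that Fisher's test on Visit 3 status is a legitimate comparison of randomised arms. That is correct; its error rate is sound. But Visit 3 frequency is already secondary endpoint 2 or 3 in sections 4.1 and 7.1, so the change endpoints would then add nothing. The same holds if every woman had the sign at Visit 0, which section 5.1 does not require.

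Three stronger readings are tempting and not supported:

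- A reader might infer that Fisher's test and exact intervals are wrong throughout section 9.1.3, or can never be used for change. They suit the other two endpoints listed, and they would suit a defined per-woman outcome.
- A reader might infer that the plan treats the two scans as independent samples and so badly misstates the standard error. Section 9.1.3 prescribes no such step; its comparison is between arms. The error would also be bounded. With assumed frequencies of 83% and 42%, the covariance is at most 0.42 − 0.83 × 0.42 = 0.0714, so the within-woman correlation is at most 0.0714/√(0.1411 × 0.2436) = 0.385. The standard error would be overstated by at most √(0.3847/0.2419) − 1 = 26%, in the conservative direction.
- A reader might take the rejection rates in the simulation as the plan's false-positive rate. They describe one possible workaround under assumed probabilities, not an instruction in the protocol.

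**Conclusion.** The mismatch is real and confined. For limited displaceability and hyperechoic linear lesions, the change endpoints as worded are paired arm-level differences or ratios, and the methods fixed for them do not estimate or test those quantities. The valid fallback, Visit 3 status alone, duplicates other endpoints and does not use the Visit 0 scan.

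Two of six secondary endpoints are affected. The primary analysis, the sample size and data collection are untouched. The conclusion rests on the wording of the protocol and on the repeated scans; it does not depend on any of the illustrative counts. It would fall away for a per-woman definition in the statistical analysis plan, which is not at hand, though the protocol text would still need to agree with it. The point should be corrected before unblinding, but it does not threaten the trial's main conclusion.

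**What to change.** In section 9.1.3, separate the two change endpoints from the other two and state for them:

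- **Between arms:** compare Visit 3 status (sign present or absent) between each dose and placebo in all ITT women, adjusted for or stratified by Visit 0 status, by an exact stratified test or logistic regression.
- **Within arms:** report the absolute change and, for limited displaceability, the percentage change descriptively. Give a paired-proportion interval for the absolute change.
- **Supportive only:** resolution among women with the sign at Visit 0, with Fisher's test and an exact interval. It should not be the main analysis, because it drops randomised women and ignores newly acquired signs in a trial of adhesion prevention.

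Align the endpoint wording in the synopsis and sections 4.1 and 7.1. Section 7.1 attaches a limit of four or fewer to the hyperechoic lesion endpoint that the other sections lack; settle what it means before present/absent is fixed as the outcome.

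Cost: text changes in four places and slightly more analysis work, with no new data. The drawback is sparse strata at about 24 women per arm. A stratum may hold no events, as in the example above; an exact stratified test copes with that better than ordinary logistic regression.

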9.1.4 Safety analysis

Descriptive part of safety analysis by primary endpoint will include evaluation of frequencies and bilateral 95% CI for the following primary endpoint parameters:

- AR – common frequency and frequency in separate groups (as per ICD-10)
- SAR - common frequency and frequency in separate groups (as per ICD-10)
- Frequency of clinically significant changes in results of physical examination – in general, for the study and by visits
- Frequency of clinically significant changes in parameters of laboratory investigations – in general, for the study and by visits
- Frequency of clinically significant changes in parameters of BP and heart rate – in general, for the study and by visits
- Frequency of clinically significant changes in ECG parameters – in general, for the study and by visits

Comparison of frequencies between main and control groups will be performed using Fisher's exact test (bilateral variant).

Analysis of the specified safety parameters will be performed for ITT and safety population (if it is different from ITT).

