Administered into serous cavity by method of single irrigation (by syringe, without injuring abdominal mesothelium) in aseptic conditions before completion of surgery. Re-administration is not recommended.

Before administration, aspirate all remaining fluids (blood, exudate, solutions administered intraoperatively).

Before use, heat the solution until body temperature.

Doses for adults:

For abdominal cavity surgery, the drug is administered at the dose of 2.4 mL/kg body weight into abdominal cavity.

For gynecological surgery, the drug is administered into abdominopelvic cavity at the dose of 1.5 to 2.4 mL/kg providing post-surgical position preventing discharge of the drug from the pelvic cavity.

For surgeries related to pericardium dissection, the drug is administered intrapericardially at the dose of 0.05 mL x left ventricular stroke output.

For administration into joint cavity during arthroscopy - up to 2 mL depending on the volume of joint.

The drug is intended only for administration into serous cavity, intravenous administration is unacceptable. Do not mix with other drugs. Do not use as a vehicle of other drugs as antibiotics, chemotherapeutic agents, etc.

Side effect

In the Phase I clinical study, general incidence of side effects on administration of the drug Seroguard was similar to those during administration of the placebo. During the study, the following side effects possibly related to administration of the drug were found: hyperthermia (1.8 %), pain in infraclavicular region (0.9 %), increased WBC count in blood (0.9 %).

Overdose

No information on overdose of the drug Seroguard is available.

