2.2.2 Clinical studies

Seroguard, solution is a new original drug that has passed pre-clinical studies, Phase I clinical study was also performed (19). Multi-center double-blind placebo-controlled study included patients of both genders at the age from 18 to 75 years having indications for planned laparoscopic cholecystectomy. Treatment group (Seroguard) included 24 patients, and placebo group (0.9% sodium chloride) - 23 patients. Seroguard, solution 0.41 g/L, JSC Pharmasyntez, Russia or its respective placebo were administered into abdominal cavity at the end of laparoscopic cholecystectomy at the dose of 2.4 mL/kg. Incidence, nature and severity of adverse reactions (including clinically significant abnormalities of physical examination, vital signs, instrumental investigations, clinical laboratory parameters) were evaluated. 206 adverse reactions (AR) were recorded in the study: 110 (53,4%) – in the group of treatment with Seroguard and 96 (46.6%) – in the placebo group. 14 cases of adverse reactions (6.8%) were moderate and one was severe, remaining adverse reactions were mild. 194 (94.2%) ARs were doubtfully related to administration of the drug, 8 (3,9%) – conditionally related, and 4 ARs (1,9%) in the treatment group were evaluated as possibly related to the drug administration. 196 of 206 ARs (95.2%) completed by recovery of patient, in the remaining 10 cases (4.9%), a significant amelioration was observed. 4 serious ARs were also recorded in three patients of both groups in the study.

No statistically significant changes, except for level of eosinophils and lymphocytes in the placebo group, were recorded in most of complete blood count and blood chemistry parameters. A statistically significant elevation ($p = 0.0297$) was noted in the level of eosinophils in the placebo group by Visit 11 (Day 28), however, it was not clinically significant. Similarly, elevation in lymphocytes ($p = 0,0148$) was observed by Visit 11 (Day 28), which was not clinically significant.

The performed analysis of coagulogram data did not reveal statistically significant differences in any parameter between the Visits ($p > 0.05$). Analysis did not also show any statistically significant variations in vital signs ($p > 0.05$).

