At the post-operative period, for all the groups patient management is performed in accordance with the established standards.

The drug is intended only for administration into serous cavity, intravenous administration is unacceptable. Do not mix with other drugs. Do not use as a vehicle of other drugs as antibiotics, chemotherapeutic agents, etc.

Selection of dosage is based on principle of Seroguard action – the drug acts at the site of its administration. Seroguard should cover the surface of abdomen in order to form an efficient liquid barrier which causes launch of apoptosis of activated fibroblasts, interrupting development of adhesive process at the site of abdomen injury.

In the studies by diZerega (22,23), area of abdomen and volume of liquid required for its complete coverage were determined. For a human being, a maximum weight coefficient is approximately 2.4 mL/kg (that is, for patient with weight of 80 kg, $80 \times 2.4 = 192$ mL minimum). Thickness of boundary layer, in which reaction to injury is developed, which causes adhesions, and in which it is necessary to block activity of kinase cascade, is about $h = 0.3$ mm based on morphometry data. Thus, the volume of boundary layer is equal to multiplication of thickness of boundary layer by area of abdomen surface ($V = S \times h$). Activity of cascades in cells of deeper layers is unfavorable to be suppressed, because of ongoing process of surgical wound healing.

For gradually released active component of IC_{50} value related to MAPK p38 fibroblasts, $IC_{50} = 300$ nM, $M = 413.9$ g ($IC_{50} = 413.9 \times 300 \times 10^{-9} = 0.00012417$ g/L = 0.12417 mg/L) (24).

Area of abdomen (approximately equal to body surface) of a person with weight of 80 kg and height of 180 cm is about 2 m². Volume of boundary layer is $2 \times 0.0003 = 0.0006$ m³ = 0.6 dm³ (the drug will be distributed at this volume).

Based on $T_{1/2}$ coding RNA for MAPK (25) for 3-day exposure (based on absence of active absorption of conjugate in abdominal cavity):

$$0.12417 \text{ mg/L} * 0.6 \text{ L} * 24 = 1.79 \text{ mg}$$

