3.2 Study objectives

1. To determine change in number of pelvic adhesions based on MRI data in post-surgical period in comparison to data of pre-surgical MRI data
2. To determine change in thickness of pelvic adhesions based on MRI data in post-surgical period in comparison to data of pre-surgical MRI data
3. To determine frequency of limited displaceability of pelvic organs in post-surgical period (based on results of transvaginal ultrasound investigation).
4. To determine frequency of hyperechoic linear lesions in post-surgical period based on results of transvaginal ultrasound investigation.
5. To determine changes in frequency of detecting limited displaceability in comparison to baseline (absolute change and in % of baseline value).
6. To determine changes in frequency of detecting hyperechoic linear lesions based on repeated transvaginal ultrasound investigation in comparison to baseline.
7. To determine frequency of detecting complete absence of USI – signs of adhesion process in pelvis in post-surgical period (defined as absence of limited displaceability of pelvic organs and absence of hyperechoic linear lesions)
8. To determine number of adhesions during surgery.
9. To determine number of dense adhesions during surgery.
10. To determine percentage of female patients with any adverse reactions.
11. To determine percentage of female patients with any serious adverse reactions.
12. To determine percentage of female patients with adverse reactions, relation of which to use of the test drug or the placebo is “definite”, “probable” or “possible”.
13. To determine percentage of female patients with serious adverse reactions, relation of which to use of the test drug or the placebo is “definite”, “probable” or “possible”.
14. To determine percentage of female patients with mild adverse reactions.
15. To determine percentage of female patients with moderate adverse reactions.
16. To determine percentage of female patients with severe adverse reactions.
17. To determine percentage of female patients with clinically significant changes in results of physical examination.
18. To determine percentage of patients with clinically significant changes in vital signs.
19. To determine percentage of female patients with clinically significant changes in electrocardiogram (ECG).
20. To determine percentage of female patients with clinically significant laboratory parameters.

4 Design of the study

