4.2.3.3 Evaluation of vital signs

Evaluation of vital signs will be performed at each visit. Acceptable terms of performance are specified in section 4.2.4. Evaluation includes:

- measurement of axillary temperature;
- measurement of systolic and diastolic blood pressure (BP);
- count of heart rate per 1 minute;
- count of respiration rate (RR) per 1 minute.

Measurements are performed in seated or semirecumbent position after 5 minutes of rest on one and the same hand (for measurement of BP and heart rate) and, if possible, by one and the same specialist of a clinical site during participation of a particular female patient in the study.

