4.2.3.4 Evaluation of local status (condition of postsurgical wounds)

To be evaluated:

- Palpatory tenderness
- Hyperemia
- Edema
- Presence of discharge

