8.1 List of safety parameters

- Vital signs (body temperature, BP, HR, RR)
- Laboratory investigations:
 - Blood chemistry – total protein, glucose, ALT, AST, total bilirubin, alkaline phosphatase, amylase, creatinine
 - Complete blood count – RBC, WBC, platelet count, hemoglobin, hematocrit, WBC differential, ESR
 - Coagulogram – coagulation time, international normalized ratio (INR), thrombin time, activated partial thromboplastin time (APTT)
 - Urinalysis – color, transparency, pH, specific gravity, protein, glucose, WBC, RBC, bacteria, casts, salts
- ECG data – heart rate [HR], PR, QRS, QT intervals and calculated QTc interval

- USI data
- Incidence of adverse reactions
- Incidence of serious adverse reactions
- Incidence of unexpected adverse reactions
- Incidence of adverse and serious adverse reactions caused treatment discontinuation/withdrawal from the study

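### Section 9.1.4 analyses only blood pressure and heart rate, although Section 8.1 lists four vital signs and objective 18 covers vital signs without restriction

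*Protocol*

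**What the plan says.** Three parts of the Protocol treat vital signs as a class of four measurements, or leave the class unrestricted.

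- Section 8.1 lists among the safety parameters "Vital signs (body temperature, BP, HR, RR"). Section 4.1 and the Synopsis give the same four.
- Section 4.2.3.3 has vital signs evaluated at each visit, including "measurement of axillary temperature" and a respiratory rate count.
- Objective 18 in Section 3.2 reads: "To determine percentage of patients with clinically significant changes in vital signs". It names no components and excludes none.

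Section 9.1.4 then sets out the outcomes to be summarised with two-sided 95% confidence intervals and compared by two-sided Fisher's exact test. Its vital-sign line is "Frequency of clinically significant changes in parameters of BP and heart rate", overall and by visit. Temperature and respiratory rate are not mentioned, and no reason is given for leaving them out.

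**The concern.** The analysis section is narrower than the parameter list and the objective it serves. A statistical analysis plan (SAP) or report that follows Section 9.1.4 literally would tabulate two of the four measured signs, and objective 18 would be answered only for those two.

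One of the omitted signs has some history with this product. For Phase I, Section 2.1 lists as possibly related effects "hyperthermia (1.8 %), pain in infraclavicular region (0.9 %), increased WBC count in blood (0.9" %). Hyperthermia is the most frequent of the three. A reader of the final report would reasonably expect temperature among the tabulated vital signs. If the line is left as it stands, whether to show temperature could be decided after the data are seen.

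**Working it through.** **1. Setting the sections side by side.**

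| Objective (Section 3.2) | Outcome in Section 9.1.4 |
|---|---|
| 17, physical examination | carried over as a whole class |
| 18, vital signs | narrowed to blood pressure and heart rate |
| 19, ECG | carried over as a whole class |
| 20, laboratory parameters | carried over as a whole class |

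Only objective 18 is cut down to named components. Of the four signs in Section 8.1, two remain (2/4). Section 8.2 adds that safety at Visits 1 to 3 is evaluated from the parameters in Section 8.1, which include temperature and respiratory rate. The narrowing is therefore out of line with the rest of the Protocol.

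**2. What the Phase I percentages count.** Section 2.2.2 gives 24 Seroguard and 23 placebo patients and 206 reactions in all, of which "110 (53,4%) – in the group of treatment with Seroguard". It also gives 4 reactions judged possibly related, all in the treatment group.

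- 2/110 = 1.8%, the printed hyperthermia figure.
- 1/110 = 0.9%, the printed figure for each of the other two effects.
- 2 + 1 + 1 = 4, and 4/206 = 1.9%, as printed in Section 2.2.2.
- Patient denominators do not fit: 1/24 = 4.2%, 2/24 = 8.3%, 1/47 = 2.1%.

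So the percentages are shares of Seroguard reactions. Hyperthermia accounts for 2 of the 4 possibly related reactions. That is at most 2 of 24 patients (8.3%), if the two reports came from different patients.

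**3. How much weight that bears.** The Protocol gives no placebo count for hyperthermia. Assuming the extreme case of 0 of 23 on placebo against 2 of 24 on Seroguard, the two-sided Fisher p-value is 0.49. Section 2.2.2 also reports no statistically significant variation in vital signs.

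**4. What a comparison could show here.** As an illustration, assume true rates of 8.3% and 2% and take the 26 patients randomized per arm.

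| Comparison | Events against zero needed for p ≤ 0.05 | Approximate power of Fisher's test |
|---|---|---|
| 26 v 26 (single arms) | 6 | 1% |
| 26 v 52 (one dose v both placebo arms) | 3 | 20% |
| 52 v 52 (both doses v both placebo arms) | 6 | 12% |

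The added temperature table would therefore be mainly descriptive. Its value lies in the frequencies and intervals.

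**5. Other routes into the analysis.** Section 9.1.4 compares adverse reactions overall and by ICD-10 group, and also physical-examination changes. A fever recorded as a reaction is counted there. The route is incomplete. Section 8.2 defines a reaction as something that may be drug-related, and its rule for turning abnormal values into reactions names laboratory and instrumental results only. Whether a raised temperature after surgery is recorded is left to the investigator.

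**The case against.** Section 9.1 describes itself as brief and leaves the complete analysis to the SAP, so the line could be read as shorthand. That would be persuasive if Section 9.1.4 had simply said vital signs. It names two components instead, in conflict with Section 8.1, so the text needs correcting whatever the SAP adds.

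Three stronger readings are tempting, and the documents do not support them.

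- *A reader might infer that temperature is never compared.* It can be, through the adverse-reaction tables. Reactions are recorded with causality grades that include unlikely, conditional and unclassified (Sections 8.2 and 8.3), and Section 9.1.4 does not restrict the comparison by causality. In Phase I, 194 of 206 recorded reactions were only doubtfully related. What is missing is a frequency analysis of the measurement itself.
- *A reader might infer that Phase I produced a temperature signal.* Two of 110 reactions, with no placebo count, do not show an excess. Section 2.1 calls the overall incidence similar to placebo.
- *A reader might infer that the same fault applies to wound healing.* "Evaluation of local status (condition of postsurgical wounds") is scheduled at Visits 1 to 3 and is absent from Section 9.1.4. But it is also absent from Section 8.1, so nothing is contradicted, and its tabulation can be left to the SAP. The sentence "Activity of cascades in cells of deeper layers is unfavorable to be suppressed, because of ongoing process of surgical wound healing", in Section 2.4, belongs to the dose calculation. Section 2.3.1 does not list impaired wound healing as a risk. Testing four wound items at three visits would add at least 4 × 3 = 12 low-power tests.

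**Conclusion.** The inconsistency is real but minor. Section 9.1.4 covers two of the four vital signs that Section 8.1 declares and the sites measure. Followed literally, it leaves objective 18 partly unanswered. Temperature and respiratory rate would enter the comparison only through a recorded adverse reaction or a physical-examination finding.

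This rests on reading Section 9.1.4 as written. The SAP was not available, and it may already list all four signs. The Phase I hyperthermia reports make it sensible to tabulate temperature, but they are not evidence of harm. The point has no bearing on the primary analysis or the sample size.

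**What to change.** In Section 9.1.4, replace the restriction to blood pressure and heart rate with vital signs as listed in Section 8.1: body temperature, blood pressure, heart rate and respiratory rate. Keep the presentation already planned, which is frequencies overall and by visit, 95% confidence intervals and two-sided Fisher's exact test. Carry the same list into the SAP before unblinding.

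Optionally, summarise local wound status by visit descriptively, with no added tests, since it is collected at Visits 1 to 3.

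The cost is one line of text and a few more safety tables. No new data are needed.
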